Sub-Committee, and disclosed in the published primary trial paper. Upon the study's completion, a formal notification will be submitted to the ethics committee within 30 days, confirming the end of the trial.

Dissemination policy

All study results, regardless of their nature, will be published in international scientific journals, assured by an unrestricted publication agreement with Zoles ApS, the insole manufacturer. Results will also be shared at both national and international conferences to ensure a broad dissemination. We are committed to adhering to the Vancouver conventions by the International Committee of Medical Journal Editors (ICMJE) for ethical authorship. The primary trial report will clearly outline, and reference all collected outcomes, directing readers to the comprehensive dissemination plan for details on unreported data or analyses. Working titles for all journal publications to be associated with this study are listed below:

- 1. The effectiveness of customised 3D-printed insoles on perceived pain, comfort, and completion time among frequent Park Runners: Study protocol for a pragmatic randomised controlled trial (The ZOLEs RCT)*
- 2. The effectiveness of customised 3D-printed insoles on perceived pain, comfort, and completion time among frequent Park Runners: A pragmatic randomised controlled trial (The ZOLEs RCT)*
- 3. The effect of customised 3D-printed insoles among frequent Park Runners with high clinically relevant running-related pain: pre-planned secondary and long-term follow-up analysis from a pragmatic randomised controlled trial (The ZOLEs RCT)*

Discussion

This study is designed to investigate the effectiveness of customised 3D printed insoles in alleviating pain, enhancing comfort, and improving completion time amongst recreational parkrun participants. The study is meticulously crafted, aligning with the FINER-criteria, ensuring it is Feasible, Interesting, Novel, Ethical, and Relevant [35].

Pain and niggles are common issues among active runners, and not only impede performance, but also potentially lead to a reduction in physical activity and an associated increase in premature mortality risk [6,13,15].

The potential of 3D customised insoles to mitigate these common issues stems from a grounded hypothesis supported by preliminary evidence [21,25,29], suggesting their effectiveness in pain reduction. The simplicity and accessibility of this intervention underscore its potential widespread applicability and adoption amongst the running community. If proven effective, these insoles could serve as a convenient and practical solution, addressing pain while enhancing the overall running experience.

The pragmatic approach of this trial is anchored in a design that maximises the utility and applicability of the findings. Every aspect, from the real-world setting to a diverse participant base, is tailored to ensure that the results are not only scientifically rigorous but also practically insightful. In a realm where pain is often a limiting factor, interventions that are both effective and easily integrable are pivotal [62].

Strengths and limitations

A major limitation of this study is the absence of blinding for the intervention, which could potentially introduce bias in the self-reported outcomes, particularly as the primary outcome, pain, is inherently subjective. This subjectivity could amplify the Hawthorne effect, leading to potential biases that are not directly attributable to the intervention itself [63]. The implementation of a sham insole or an off-the-shelf comparator could have mitigated this

limitation by providing a control for the placebo effect and the subjective improvement due to participants' awareness of the treatment. However, this study is designed with a pragmatic perspective that aligns with real-life scenarios where no sham insole would be offered to a potential customer or patient.

We acknowledge the potential impact of a 'pleasing effect' but chose not to blind the hypothesis for the participants because the primary motivation for seeking orthotics in real-world contexts is often pain mitigation. We aim for the study results to be as applicable as possible to these real-world scenarios, and thus, accepting this limitation was a considered decision to enhance the external validity and practical applicability of our findings. The study is designed to evaluate the effectiveness of the insoles in conditions that closely mimic the everyday experiences and choices of runners seeking solutions for pain relief.

Despite these challenges, the study's structure and methodology have been meticulously crafted to yield insights that are both scientifically rigorous and practically insightful, balancing between the ideal conditions for experimental control and the complexities of real-world application. Conversely, this study boasts several strengths that bolster its reliability and validity. The use of blinded group allocation sequence, external outcome assessors who are blinded to the group assignments, and an external data manager also blinded to group allocation ensures objectivity in data collection and analysis, minimizing bias. Furthermore, the recording of all outcomes in participants' natural environments, including baseline data, amplifies the real-world applicability of the findings. Participants are thus not influenced by the study personnel, ensuring the outcomes reflect the real-life effect of the intervention, enhancing the study's external validity. Additionally, the employment of a mobile scanning unit allows us to recruit participants from more distant parkrun locations, thus allowing for enrolment of participants who might not have the means to travel across London to partake in this study.

The intention to treat analysis in the primary study report ensures all participants are included in the final analysis, maintaining the randomisation benefits and offering a conservative estimate of the intervention's effectiveness. The step-wedge design addition enhances the study's robustness, allowing immediate verification of effectiveness by comparing the control group's response post-primary trial period to the intervention. The inclusion of a 52-week post-market surveillance further elevates the study's comprehensiveness, offering insights into the long-term effects and usability of the insoles.

Transparency is maintained through pre-registration of the study and the detailed description of the intervention using the TIDieR checklist [45], ensuring replicability and openness in reporting. The publication of this study protocol underscores the commitment to transparent and ethical research practices, contributing to the broader scientific discourse and public scrutiny.

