- a) Individuals with severe foot deformities will be excluded during the foot scanning process if the level of customization needed exceeds what is possible via the Zola software.
- b) Individuals with uncontrolled diabetes with foot complications, or other conditions that might interfere with their ability to safely use the insoles and participate in running activities. Evaluated via the Physical Activity Readiness Questionnaire Plus (PAR-Q+) at inclusion.

Interventions

By virtue of being a pragmatic trial, all participants will be allowed to use or keep using any treatment or concomitant care, regardless of their group allocation. Pre-existing use of insoles in the intervention group, should naturally be replaced by this study's intervention.

Experimental: ZOLES Customised 3D-printed insoles

Participants allocated to the intervention group will receive customised 3D-printed insoles (Zoles ApS, Esbjerg, DK-3060, Denmark) to mitigate running-related pain and discomfort

(Figure 1). Being a pragmatic trial, all participants are permitted to continue or initiate any usual care of their choice.

Based on measurements from a 3D scanning procedure (Figure 2), and factoring in individual data such as age, weight, and activity preferences, custom insoles are designed using the ZOLA software. The insoles are then 3D-printed by Zoles ApS in Esbjerg (Denmark), using BCN3D printers (Barcelona, Spain) and a TPU (Thermoplastic Polyurethane) filament material from Recreus (Alicante, Spain). The printed insoles are tailored for optimal support, performance, and comfort, with varying densities for areas like the arch and heel. They are finished with an OnSteam® microfiber cover for added durability and comfort. The insoles are intended for regular insertion into participants' shoes to align with their unique biomechanical needs. (Information translated and adapted from [47]). The participants are recommended to gradually wear the insoles in over a three-week period (Appendix D) but are otherwise encouraged to use the insoles within all their different shoes, and to wear these during all activities of daily living and during their running activities. Adherence to the intervention is not controlled but simply collected over the duration of the trial.

A thorough description of the intervention following the TIDieR guidelines [45], including reasons for potential needs for modifications of the insoles is included (Appendix B).

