- **Running-related injuries:** The incidence rate of injuries related to running will be monitored and reported as the number of injuries for every 1000 hours of running exposure over the 10-week duration.
- **Time-loss:** The total number of days participants miss out from running due to pain, discomfort, or injury will be tracked weekly for 10 weeks, and again at the 18-week mark.
- **Weekly Mileage:** The distance participants run every week will be recorded during the 10-week trial period, and again at the 18-week mark.
- **Weekly running exposure:** The total time participants spend running every week will be obtained in hours and minutes for the 10-week trial period, and again at the 18-week mark.
- **Adherence to intervention, ADL%:** This outcome tracks how frequently participants use the Zoles insoles for everyday activities such as sitting, standing, walking, and driving over the 10 weeks, and tracked again at the 18-week mark, and at the 52-week post-market surveillance.
- **Adherence to intervention, RUN%:** The percentage of time participants wear the Zoles insoles specifically during running will be monitored over the 10 weeks, and again at the 18-week mark, and at the 52-week post-market surveillance.
- **Adverse events from using Zoles insoles:** All adverse events associated with the usage of Zoles will be reported based on their type and number. Throughout the trial, participants will be encouraged weekly to report any adverse events through the trial

hotline. Participants will be asked again at the 52-week-post-market-surveillance to capture any long-term events.

Other Outcomes

The other outcomes of interest for the pre-planned secondary subgroup analyses include:

- **Participants achieving MCID reduction in pain:** This measure looks at the percentage of participants who manage to achieve a clinically meaningful reduction in running-related pain, defined as a reduction equal to or larger than the MCID (NRS \geq 2) as described by Salaffi et al. [48] over the 10 weeks.
- **Time until MCID reduction in pain:** This outcome gauges the time in weeks it takes for participants with clinically significant pre-existing pain (NRS \geq 3 as defined by Rathleff et al. [38]) to achieve the clinically meaningful reduction in running-related pain (MCID) during the 10-week trial period.

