The allocation phase (Timepoint 0) commences post-enrolment, where participants are sent a baseline questionnaire. The information gathered from this questionnaire is used in the balanced block randomisation procedure. Upon completion of the baseline questionnaire, participants are set up to receive weekly follow-up surveys during the primary study period (Weeks 1-10). During this period, there is weekly follow-up on primary and secondary outcomes, delivery of allocated intervention group insoles projected before week 3, and weekly monitoring of adherence and adverse effects. In a case where a pair of insoles do not fit inside a participant's footwear, a fast-track adjustment, production, and shipment procedure takes place, ensuring a minimal delay of insole delivery of approximately one week.

In the control group step allocation period (Weeks 10-18), control group participants receive their customised insoles and all participants are sent a single event follow-up questionnaire at week 18. This questionnaire covers primary and secondary outcomes, as well as adherence and adverse effects.

Finally, post-market surveillance occurs at Timepoint Week 52, a year after the study's commencement. All participants receive a follow-up questionnaire assessing their post-trial experiences with the insoles, any adverse effects experienced during the year, and the long-term effects of the Zoles insoles (Figure 3).

Sample size

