The trial will include prospective data collection using e-mail-distributed surveys via REDCap (Vanderbilt University, Nashville, TN, USA). Participants receive these surveys weekly for the initial 10 weeks, facilitating the collection of real-time data on their experience, pain levels, and the impact of the customised insoles for those in the intervention group. At the conclusion of this primary trial period (week 10), participants in the control group are provided with their customized insoles, marking the commencement of an additional 8-week observation period to compare intervention response between both groups (week 18). The final follow-up occurs at the 52-week mark, again via REDCap to provide insights on their long-term experiences, adverse effects, and the sustained impact of the Zoles insoles on their running-related pain and comfort.

Reminders will automatically be sent to participants at 24 hours and 48 hours after the original time of a follow-up questionnaire to participants failing to respond. Investigators will contact participants via telephone and SMS after another 24 hours if still not responding after receiving reminders to reduce the amount of missing data.

Data management

Every participant is assigned a unique identification number, ensuring their anonymity throughout the study in compliance with the General Data Protection Regulations (GDPR) under the Data Protection Act 2018.

Data collection, both at baseline and throughout the prospective stages, is facilitated via REDCap, a secure and robust online platform renowned for its data management capabilities [56]. This process is overseen from Department of Clinical Medicine at Aalborg University (DK-9220, Aalborg Øst, Denmark) by a dedicated data handler (CD), who remains blinded to group allocation. CD and FGL constitute the Data Monitoring Committee. A list of responding and non-responding participants is generated weekly, wherefrom a list of non-responding participants to contact is generated.

The Study Director (FGL) will maintain a secured key to the participants' identities, stored on a two-factor secured personal drive, ensuring the capability to identify and withdraw individual data if necessary.

All data is safeguarded within GDPR compliant two-factor and password-protected systems at St. Mary's University server, and on the REDCap online system. These measures ensure that the data remains inaccessible to unauthorized personnel, preserving confidentiality.

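### Weekly adverse-event prompting is scheduled only to week 10, when the control group first receives insoles, so early harms in half of the planned users are followed less closely

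*Combined protocol and SAP*

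**What the plan says.** The adverse-event item under Secondary outcomes states: "Throughout the trial, participants will be encouraged weekly to report any adverse events through the trial" hotline. It then adds: "Participants will be asked again at the 52-week-post-market-surveillance to capture any long-term events". It does not mention week 18.

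Participant timeline puts "weekly monitoring of adherence and adverse effects" inside the primary study period, weeks 1 to 10. For weeks 10 to 18 it says that "all participants are sent a single event follow-up questionnaire at week 18", and that this questionnaire includes adverse effects. Procedures and data collection agrees on the weekly phase: "Participants receive these surveys weekly for the initial 10 weeks". On the control arm it says: "At the conclusion of this primary trial period (week 10), participants in the control group are provided with their customized insoles".

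On first use, the Interventions section says: "The participants are recommended to gradually wear the insoles in over a three-week period". Harms makes capture depend on participants volunteering reports, with a reminder at each contact, and keeps the reporting window open from the start of insole use to one year. Statistical methods says only that adverse events will be shown by kind and count. It names no split by arm, period or exposure.

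**The concern.** Fit problems, new aches and minor injuries are most to be expected while people are getting used to an insole. The intervention arm passes through that phase with a contact every week. The control arm passes through it just after weekly contact has stopped. Because the Harms section relies on volunteered reports prompted at contacts, fewer contacts mean fewer prompts and a longer recall period, and short-lived events are the ones most easily lost.

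What is at stake is the description of harms in the control half of the users, and any summary that joins or compares the two halves. The plan also intends to look at benefit in controls once they have insoles (secondary objective 2). It would be unbalanced to present benefit in late recipients while observing their harms much less closely. Harms also sets a 7-day limit, counted from occurrence, for reporting serious unexpected events to the ethics sub-committee. Between widely spaced questionnaires, meeting that limit depends on the participant ringing in unprompted.

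**Working it through.** The plan gives no figure to reproduce here. The check is a count of scheduled adverse-event contacts after first receipt of the insoles.

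**Inputs**
- Scheduled contacts: weeks 1 to 10, then 18 and 52 (Participant timeline; Procedures and data collection).
- Intervention delivery: projected before week 3 (Participant timeline). I take week 2, with week 3 as a late case.
- Control delivery: week 10 (Procedures and data collection).
- Wear-in: three weeks (Interventions), assumed to apply to controls as well.
- Group size: 100 per arm, 200 in total (Sample size).

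**Rule.** For delivery in week *s*, count contact weeks *w* with *s* < *w* ≤ *s* + 3 for wear-in, *s* < *w* ≤ *s* + 8 for the first 8 weeks, and *s* < *w* ≤ 52 for the whole period.

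| | Intervention, *s* = 2 | Intervention, *s* = 3 | Control, *s* = 10 |
|---|---|---|---|
| Wear-in | weeks 3–5: 3 | weeks 4–6: 3 | weeks 11–13: 0 |
| First 8 weeks | weeks 3–10: 8 | weeks 4–10: 7 | week 18: 1 |
| To week 52 | 8 + 2 = 10 | 7 + 2 = 9 | weeks 18, 52: 2 |

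**Share of users affected:** 100/200 = 50%.

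**Participant-contacts in the first 8 weeks of use,** at full enrolment and retention: 100 × 8 = 800 in the intervention arm (100 × 7 = 700 with week-3 delivery) against 100 × 1 = 100 in the control arm.

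**Gaps between scheduled contacts after hand-over to controls:** 18 − 10 = 8 weeks, then 52 − 18 = 34 weeks. In the intervention arm's first 8 weeks (delivery in week 2) the gap is 1 week.

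The adverse-event row of Figure 3 is blank in the text available, as are both intervention rows, so shading has probably been lost. The figure is used only for its time points. The questionnaires and leaflets in the appendices are listed but not reproduced, so any reporting instructions in them are unknown.

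**The case against.** The strongest reply is that the sections do not conflict. A reader might infer that the outcome definition and the schedule cannot both be carried out. The documents do not support that. The same outcome list uses the word trial for the 10-week period, the adverse-event item separates its weekly phase from the 52-week survey, and Other Outcomes describes that survey as coming after the trial. Read this way, the item agrees with Participant timeline. Against that, the abstract says the trial includes the 52-week surveillance, and most neighbouring outcomes carry an explicit time limit that this one lacks. The wording is ambiguous rather than contradictory, and the benign reading leaves the difference in contacts where it was.

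Second, control harms are not left uncaptured. No section closes the hotline at week 10, week 18 asks every participant about adverse effects, and week 52 asks again. Handing over the insoles may itself be a contact at which a reminder is given. All of this stands, and it is why incomplete recording is likely rather than certain. None of it supplies a scheduled prompt between hand-over and week 18.

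Third, the plan does not say it will pool adverse events across arms or periods, and it plans no test between arms. That also stands. The risk is conditional on how the tables are built, which the plan leaves open.

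Fourth, extra prompts cost effort and create an imbalance. Procedures and data collection follows non-response with automatic reminders, then telephone and SMS. Repeating that for about 100 people over 8 weeks would take staff time, so the prompt should go out without the chasing, at the price of somewhat lower response. Controls would also have more contact than the intervention arm in weeks 10 to 18, just before a comparison of self-reported outcomes. This is a small drawback, since it gives controls what the intervention arm had in its own first 8 weeks, but it should be declared.

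**Conclusion.** The concern holds as a difference in how closely harms are observed. In the first 8 weeks of use, controls have 1 scheduled adverse-event questionnaire against about 8 (7 with week-3 delivery). During wear-in they have 0 against 3. This affects half of the planned users. Transient events in controls are likely to be recorded less completely, and an adverse-event frequency pooled over all users, or compared between early and late recipients, would mix two intensities of capture.

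The size of any under-count cannot be given, because the documents contain no event rate and no recording probability. A reader might also infer that the main trial result is biased. It is not: controls have no Zoles insoles before week 10, so the randomised 10-week comparison is untouched.

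The counts assume delivery in week 2 or 3 for the intervention arm and hand-over at week 10 for controls. If hand-over to controls slips, week 18 is still their only scheduled contact before week 52, but it falls earlier in their use of the insoles.

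**What to change.** 1. Send controls a short automated weekly REDCap e-mail from hand-over to week 18, limited to the adverse-event prompt and the two adherence items, without telephone or SMS follow-up.
2. In the adverse-event item under Secondary outcomes, state the week in which weekly prompting ends and add the week-18 contact, so that it agrees with Participant timeline.
3. In Statistical methods, specify that adverse events are tabulated by arm and by weeks since hand-over, with the contact schedule stated beside the table.

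**Cost.** Up to eight short e-mails to about 100 participants, a change to the REDCap schedule, and notification to the ethics sub-committee and the registry, which the plan already foresees for modifications. No extra staff or visits are needed if non-responders are not chased. The additional contact for controls in weeks 10 to 18 should be noted wherever week-18 results are compared between arms.

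**Timing.** Enrolment began on 16 September 2023. Ten weeks (70 days) later is 25 November, 59 days after the protocol date of 27 September, so the change was practicable when this version was written. If the extra prompts cannot be sent, items 2 and 3 still cost almost nothing and make the difference in capture visible.

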5. To assess pre-trial expectations and post-trial experiences regarding the therapeutic effects of the Zoles insoles and understand their influence on the efficacy of the intervention within the specific subgroup of participants with high baseline pain levels.

Methods

Trial design

The ZOLES trial is a pragmatic, outcome assessor blinded, randomised, controlled, superiority trial, with a two-group parallel design, and a 1:1 allocation ratio. Frequent recreational runners will undergo foot scanning and thereafter be randomised to either receive a customised 3D-printed insole (Zoles ApS, Esbjerg, DK-3060, Denmark), or to be in a “do-as-usual” control group. The pragmatic design and pre-planned secondary analyses are heavily inspired by the SExSI trial [39].

The trial protocol is based on the "PREPARE Trial guide" [35] and adheres to the "SPIRIT 2013 explanation and elaboration: guidance for protocols of clinical trials" [40] and SPIRIT checklist (Appendix A). The trial report will follow the “REPORT guide” [41], and thus adhere to the CONSORT guidelines for reporting parallel group randomised trials [42], using the CONSORT extension for pragmatic trials [43], as well as the updated CONSORT-Outcomes 2022 extension [44]. The TIDieR template (Appendix B) is used to describe the intervention to aid future replication [45].

The study was approved by the St Mary’s University Ethics Sub-Committee on 4 August 2023, and the trial was pre-registered at ClinicalTrials.gov on 4 September 2023 (ID: NCT06034210) [46], before the first participant was enrolled on September 16, 2023.

Study setting

Participant screening and enrolment for this study is undertaken from Faculty of Sport, Technology and Health Sciences at St Mary’s University (Twickenham, London, United Kingdom), with recruitment to the trial being carried out at local parkrun communities, primarily from Bushy Park (Richmond upon Thames, London, United Kingdom).

Eligibility criteria

Inclusion criteria

- a) Participant is ≥ 35 years old at commencement of trial.
- b) Participant can read, speak, and understand English.
- c) Participant can receive e-mails and complete online questionnaires.
- d) Participant is a frequent runner who participate in regular parkrun activities.
- e) Participant is capable of running at commencement of trial.

Exclusion criteria

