- **Change among participants with high baseline pain:** For participants who start the trial with clinically significant pain (NRS \geq 3) [38], their specific change in pain over the 10 weeks will be captured using a numeric rating scale from 0 (No pain at all) to 10 (Worst pain imaginable) [48].
- **Pre-trial intervention expectations:** Before the trial begins, participants will indicate their expectations regarding the therapeutic effect of the Zoles insoles on running-related pain, 5-k completion time, and footwear comfort using a 5-point Likert scale.
- **Post-trial intervention experiences:** After the trial, participants will be asked about their experiences with the Zoles intervention, indicating whether it met, exceeded, or did not meet their initial expectations via a 5-point Likert scale.
- **Post-market surveillance:** One-year post-trial, all participants (from both control and intervention groups) will be surveyed to assess the long-term effects and benefits of the Zoles insoles. This survey will include the primary outcome and all key secondary outcomes, allowing for a comprehensive evaluation over a longer period.

Participant timeline

Participants are first recruited at the finish line of local parkruns on Saturday mornings during the enrolment phase (Timepoint -1). Those interested are invited to invited to the Biomechanics Laboratory of the Faculty of Sport, Technology, and Health Sciences at St Mary's University in Twickenham, London, UK, or to an in-field assessment (for the North London area). Here, they receive detailed oral and written information about the study, and if willing to proceed, sign the written informed consent form. On this day of enrolment, participants also have their feet scanned, initiating the process that customises and orders their insoles on the spot.

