| | Enrolment | Allocation | Primary Study Period | | | | | | | | | | | |
| TIMEPOINT (weeks) | -1 | 0 | 1 | 2 | 3 | 4 | 5 | 6 | 7 | 8 | 9 | 10 | 18 | 52 |
| ENROLMENT: | | | | | | | | | | | | | | |
| Eligibility screen | X | | | | | | | | | | | | | |
| Informed consent | X | | | | | | | | | | | | | |
| Foot scanning | X | | | | | | | | | | | | | |
| 3D printing of insoles | X | | | | | | | | | | | | | |
| Group allocation | | X | | | | | | | | | | | | |
| INTERVENTIONS: | | | | | | | | | | | | | | |
| Intervention (Zoles) | | | | | | | | | | | | | | |
| Control ("do-as-usual" until week 10) | | | | | | | | | | | | | | |
| ASSESSMENTS: | | | | | | | | | | | | | | |
| Baseline/end of study questionnaire | | X | | | | | | | | | | | | X |
| Outcome questionnaire | | | | | | | | | | | | | X | |
| 1. Running-related pain | | | X | X | X | X | X | X | X | X | X | X | X | |
| 2. GROC | | | X | X | X | X | X | X | X | X | X | X | X | |
| 3. Foot/footwear comfort | | | X | X | X | X | X | X | X | X | X | X | X | |
| 4. 5km completion time | | | X | X | X | X | X | X | X | X | X | X | X | |
| 5. Running-related injuries | | | X | X | X | X | X | X | X | X | X | X | X | |
| 6. Time-loss from running | | | X | X | X | X | X | X | X | X | X | X | X | |
| 7. Weekly milage | | | X | X | X | X | X | X | X | X | X | X | X | |
| 8. Weekly running exposure | | | X | X | X | X | X | X | X | X | X | X | X | |
| ADHERENCE: | | | | | | | | | | | | | | |
| Adherence to intervention | | | | | X | X | X | X | X | X | X | X | X | X |
| ADVERSE EVENTS: | | | | | | | | | | | | | | |
| Adverse events from using insoles | | | | | | | | | | | | | | |

Figure 4

Appendices

A

SPIRIT checklist

B

TIDieR intervention Checklist

C

Intervention leaflet 1

D

Intervention leaflet 2

E

Participant consent materials

F

Baseline questionnaire

G

Weekly follow-up questionnaire

H

WHO Trial Registration Data Set (Version 1.3.1)

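### The rating of the insoles against expectations is scheduled only at week 52, 42 weeks after the week-10 effect it is meant to help explain

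*Combined protocol and SAP*

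**What the plan says.** Secondary objective 5 reads in part: "To assess pre-trial expectations and post-trial experiences regarding the therapeutic effects of the Zoles insoles". It also asks how these influence the efficacy of the insoles in runners with high baseline pain.

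Other Outcomes defines the experience item as a 5-point rating of whether the insoles fell short of, matched or surpassed what the runner first expected. Its timing is loose: "After the trial, participants will be asked about their experiences with the Zoles intervention". No week is given.

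The Participant timeline section does give one. It states that "post-market surveillance occurs at Timepoint Week 52", counted from the start of the study, and then: "All participants receive a follow-up questionnaire assessing their post-trial experiences with the insoles". In Figure 3 the row "Baseline/end of study questionnaire" is marked at weeks 0 and 52 and nowhere else. The week-18 survey is described without the item: "This questionnaire covers primary and secondary outcomes, as well as adherence and adverse effects". Experience against expectations is classed as an other outcome, neither primary nor secondary.

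The section on statistical methods for the secondary subgroup analysis aims at the immediate effect in participants with NRS of 3 or more at baseline. It plans regression models with expectations, experiences and adherence as covariates.

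**The concern.** The effect to be explained is the pain change over the first 10 weeks. A rating given at week 52 also takes in everything that happened afterwards: wear of the insoles, later injuries, and continued or abandoned use. It asks the runner to judge against expectations stated about a year before. The two arms answer after different lengths of use, because controls receive insoles only once the 10 weeks are over. If that rating is entered as an explanatory variable for the week-10 effect, the explanatory variable comes after the outcome and may partly be caused by it.

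The stake is limited to an exploratory objective reserved for a second publication. The primary result is not touched.

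**Working it through.** **Inputs**
- Effect time point: week 10, about 8 weeks after receipt (Objectives, time frame).
- Intervention insoles: delivery projected before week 3, taken as about week 2 (Participant timeline).
- Control insoles: provided at the end of week 10, followed by an 8-week observation period to week 18 (Procedures and data collection).
- Experience item: week 52 (Participant timeline, Figure 3).
- Expectations: recorded before the trial begins (Other Outcomes).

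**Reproducing the plan's figure.** Use in the intervention arm at week 10 is 10 - 2 = 8 weeks, which agrees with the stated figure of about 8.

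**Timing of the rating**
- Gap from the week-10 effect: 52 - 10 = 42 weeks, or 42/52 = 0.81 of a year.
- Gap from the recorded expectations: 52 - 0 = 52 weeks, about one year.
- Gap from the week-18 survey: 52 - 18 = 34 weeks.

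**Use when the rating is given**
- Intervention: 52 - 2 = 50 weeks (49 if delivery is at week 3).
- Control: 52 - 10 = 42 weeks at most. If control delivery takes 1 to 3 weeks (my assumption; the plan gives no figure), use is 41 to 39 weeks.
- Difference with intervention delivery at week 2: 50 - 42 = 8 weeks, rising to 50 - 39 = 11. The ratio is 50/42 = 1.19, rising to 50/39 = 1.28.

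**Matched alternative already in the schedule**
- Intervention at week 10: 10 - 2 = 8 weeks of use.
- Control at week 18: 18 - 10 = 8 weeks of use (7 to 5 if control delivery takes 1 to 3 weeks).

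**Competing wording of the final survey.** Other Outcomes places post-market surveillance at "One-year post-trial, all participants", whereas Participant timeline counts 52 weeks from commencement. Read literally, the former means week 10 + 52 = 62 or week 18 + 52 = 70. The gap from the week-10 effect would then be 52 or 60 weeks instead of 42.

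**The case against.** The strongest reply is that a single week-52 measurement is an inference. Other Outcomes fixes no week, the plan elsewhere uses the word trial for the 10-week period, and Procedures and data collection describes the weekly surveys as "facilitating the collection of real-time data on their experience, pain levels, and the impact of the customised insoles for those in the intervention group". The same section calls the week-52 content long-term experiences. The questionnaires themselves are listed only by title. This stands in part: the text does not rule out an earlier question. But the weekly remark is general and names no rating against expectations, and week 52 is the only week attached to the post-trial item.

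A reader might infer that objective 5 as a whole rests on year-old recall. The documents do not support that. Expectations, the other half of the objective, are recorded before the trial. Nothing asks runners at week 52 to recall their state at week 10. The one thing recalled from about a year back is what they first expected.

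A reader might also infer that the trial cannot describe experience at its primary endpoint at all. That is contradicted: pain, footwear comfort and global rating of change are collected weekly to week 10 and again at week 18, and adherence is tracked. Only the explicit rating against expectations is absent from week 10.

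The unequal use matters less than it may seem, because no between-arm comparison of the ratings is planned. Nor can more missing data be assumed at week 52: permanent dropout can only accumulate, but questionnaire non-response may come and go, and the plan gives only the 15% overall dropout figure.

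Finally, asking earlier does not by itself make experience a valid covariate. Controls have no insoles before week 10, a control rating at week 18 comes after the modelled outcome, and at any week the rating is post-randomisation. This stands in full and shapes the fix.

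**Conclusion.** The concern holds as a minor design improvement. On the best-supported reading, the rating against expectations is taken 42 weeks after the week-10 effect to which the subgroup analysis would relate it, and after about 50 weeks of use against at most 42. No such rating is scheduled at week 10, although both arms pass a point of about 8 weeks of use at surveys that are already sent.

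This rests on three assumptions: that the item is not also in a questionnaire whose contents are not in the text, that intervention insoles arrive at about week 2, and that control insoles arrive promptly at week 10. The planned use of experience as a covariate in the between-group model is unsound whichever week is chosen, since the variable is undefined for controls at week 10 and may be a consequence of the pain change.

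**What to change.** 1. State the week or weeks at which the experience item is asked, and reconcile Other Outcomes, Participant timeline, Procedures and data collection, and Figure 3, including whether the final survey is counted from the start or the end of the trial.
2. Add the existing 5-point item to the week-10 survey for the intervention group and to the week-18 survey for controls. Place it after the pain item so that it cannot colour the primary score. Keep the week-52 item as the long-term rating.
3. For objective 5, report the 8-week ratings descriptively by arm. Relate them to the week-10 pain change only within the intervention arm, and call the result an association. Do not enter experience as a covariate in the between-group effect model.

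The cost is one question in two surveys that already go out, so slightly longer questionnaires, plus a short protocol modification. It was feasible at protocol version 1: that version is dated 27 September 2023, 11 days after the first enrolment on 16 September (27 - 16 = 11), so no participant could have reached week 10.
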